16.3 Appendix 3: Specific Renal Alert Criteria and Actions and Event Follow-up

Table 16-5 Specific Renal Alert Criteria and Actions

Renal Event	Actions	
Confirmed serum creatinine increase 25 –	Consider causes and possible interventions	
49%	Follow up within 2-5 days	
Serum creatinine increase ³ 50 % +	Consider causes and possible interventions	
	Repeat assessment within 24-48h if possible	
	Consider participant hospitalization and specialized treatment	
New onset dipstick proteinuria ≥ 3+	Consider causes and possible interventions	
OR	Assess serum albumin & serum total protein	
Protein-creatinine ratio (PCR) ≥ 1g/g Cr (or mg/mmol equivalent as converted by the measuring laboratory)		
New onset hematuria ≥ 3+ on urine dipstick	Repeat assessment to confirm	
	Distinguish hemoglobinuria from hematuria	
	Urine sediment microscopy	
	Assess sCr	
	Exclude infection, trauma, bleeding from the distal urinary tract/bladder, menstruation	
	Consider bleeding disorder	

Additional specialized assessments are available to assess renal function or renal pathology.

Whenever a renal event is identified, a detailed participant history and examination are indicated to identify and potentially eliminate risk factors that may have initiated or contributed to the event:

- Blood pressure assessment (after 5-minute rest, with an appropriate cuff size
- Signs and symptoms like fever, headache, shortness of breath, back or abdominal pain, dysuria or hematuria, dependent or periorbital edem
- Changes in blood pressure, body weight, fluid intake, voiding pattern, or urine outpu

• Concomitant events or procedures such as trauma, surgical procedures, cardiac or hepatic failure, contrast media or other known nephrotoxin administration, or other diseases or causes, e.g., dehydration due to delirium, tumor lysis

Table 16-6 Follow-up of renal events

FOLLOW-UP OF RENAL EVENTS

Assess, document and record in CRF

- Urine dipstick and sediment microscopy evidence of DIN: crystals, red blood cells (dysmorphic/glomerular vs. non-dysmorphic/non-glomerular), white blood cells, tubular epithelial cell
- Blood pressure and body weigh
- Serum creatinine, BUN, electrolytes (sodium, potassium, phosphate, calcium), bicarbonate and uric aci
- Urine output

Review and record possible contributing factors to the renal event (co-medications, other co-morbid conditions) and additional diagnostic procedures (MRI etc.) in the CRF

Monitor participant regularly (frequency at investigator's discretion) until -

- Event resolution: sCr within 10% of baseline or PCR < 1 g/g Cr, or ACR <300 mg/g Cr o
- Event stabilization: sCr level with ±10% variability over last 6 months or protein-creatinine ratio stabilization at a new level with ±50% variability over last 6 months
- Analysis of urine markers in samples collected over the course of the DIN event

16.4 Appendix 4: ECG Alert Threshold Values

	Patients 18-30 years	Patients Adult > 30 years *
Resting heart rate Sinus rhythm [bpm]	HR < 30 and a HR decrease ≥ 25% HR > 130	HR < 40 and a HR decrease ≥ 25% HR > 120
QRS duration:		
=> No previous BBB **	> 120 and increase > 25% compared to (predose) baseline	> 120 and increase > 25% compared to (predose) baseline
=> Previous complete BBB * (>120 msec)	> 140 msec	> 140 msec
QTcF	QTcF > 500 msec QTcF increase > 60 msec ***	QTcF > 500 msec QTcF increase > 60 msec ***
Rhythm	Ventricular tachycardia	Ventricular tachycardia
Conduction	New complete heart block (Grade III AV block) Mobitz II AV block	New complete heart block (Grade III AV block) Mobitz II AV block

^{*} Values displayed also correspond to Severe AE ** BBB = Bundle Branch Block *** Normal QTcF with QTc increase > 60 ms may indicate cardiac and non-cardiac pathology, e.g. hypothermia, new BBB, MI. cardiomyopathy or carditis.

16.5 Appendix 5: Medications with a Known Risk of Torsades de Pointes

Table 16-7 Medications with a Known Risk* of Torsades de Pointes

Generic name	Brand name	TdP Risk
Aclarubicin	Aclacin and others	known
Amiodarone	Cordarone and others	known
Anagrelide	Agrylin and others	known
Arsenic trioxide	Trisenox	known
Astemizole	Hismanal	known

Generic name	Brand name	TdP Risk
Azithromycin	Zithromax and others	known
Bepridil	Vascor	known
Cesium Chloride	Energy Catalyst	known
Chloroquine	Aralen	known
Chlorpromazine	Thorazine and others	known
Chlorprothixene	Truxal	known
Cilostazol	Pletal	known
Ciprofloxacin	Cipro and others	known
Cisapride	Propulsid	known
Citalopram	Celexa and others	known
Clarithromycin	Biaxin and others	known
Cocaine	Cocaine	known
Disopyramid	Norpace	known
Dofetilide	Tikosyn	known
Domperidone	Motilium and others	known
Donepezil	Aricept	known
Dronedarone	Multaq	known
Droperidol	Inapsine and others	known
Erythromycin	E.E.S. and others	known
Escitalopram	Cipralex and others	known
Flecainide	Tambocor and others	known
Fluconazole	Diflucan and others	known
Gatifloxacin	Tequin	known
Grepafloxacin	Raxar	known
Halofantrine	Halfan	known
Haloperidol	Haldol and others	known
Hydroquinidine (Dihydroquinidine)	Serecor	known
Hydroxychloroquine	Plaquenil and others	known
Ibogaine	r iaqueriii and others	known
Ibutilide	Corvert	known
Levofloxacin	Levaquin and others	known
Levomepromazine (Methotrimeprazine)	Nosinan and others	known
Levomethadyl acetate	Orlaam	known
Levometriadyr acetate Levosulpiride	Lesuride and others	
Levosuipinue Mesoridazine	Serentil	known
Methadone		known
Moxifloxacin	Dolophine and others Avelox and others	known
		known
Nifekalant Ondonastron	Shinbit	known
Ondansetron	Zofran and others	known
Oxaliplatin	Eloxatin	known
Papaverine HCl (Intracoronary)	5	known
Pentamidine	Pentam	known
Pimozid	Orap	known
Probucol	Lorelco	known
Procainamide	Pronestyl and others	known
Propofol	Diprivan and others	known

Generic name	Brand name	TdP Risk	
Quinidine	Quinaglute and others	known	
Roxithromycin	Rulide and others	known	
Sevoflurane	Ultane and others	known	
Sotalol	Betapace and others	known	
Sparfloxacin	Zagam	known	
Sulpiride	Dogmatil and others	known	
Sultopride	Barnetil and others	known	
Terfenadine	Seldane	known	
Terlipressin	Teripress and others	known	
Thioridazine	Mellaril and others	known	
Vandetanib	Caprelsa	known	

^{*} This is a non-exhaustive list, updated information are listed in www.qtdrugs.org

16.6 Appendix 6: Antidepressants recommended to be used as background therapy during the study

Generic Name
SELECTIVE SEROTONIN REUPTAKE INHIBITORS (SSRIs)
Fluoxetine Fluoxetine delayed release
Paroxetine Paroxetine controlled release
Sertraline
SELECTIVE NOREPINEPHRINE REUPTAKE INHIBITORS (SNRIs)
Desvenlafaxine Desvenlafaxine Extended Release
Duloxetine
Levomilnacipran
Venlafaxine
NOREPINEPHRINE-DOPAMINE REUPTAKE INHIBITORS
Bupropion
SEROTONIN NOREPINEPHRINE RECEPTOR AGONISTS
Mirtazapine
SEROTONINE 2 ANTAGONIST/ REUPTAKE INHIBITORS
Trazodone*
MULTIMODAL ANTIDEPRESSANT/MULTIPLE SEROTONERGIC ACTIONS
Vilazodone
Vortioxetine
TRICYCLIC ANTIDEPRESSANTS
Amitripthyline*
Amoxapine
Desipramine
Doxepin
Imipramine
Nortriptyline*

Protriptyline		
Trimipramine		

Table adapted from FDA Approved Drugs to Treat Major Depressive Disorder (MDD). 2021

^{*} Ensure that the prohibited time window before and after study drug injection is respected, as indicated in Table 6-2 (Prohibited Medications and Treatment)

**Document History – Changes compared to previous final version of SAP**

Date	Time point	Reason for update	Outcome for update	Section and title impacted (Current)
16-Jan-2024	Prior to DB lock	Amendment 01 version	
[REDACTED]
 
Defined analysis window of ECG;
 
In case of multiple records in the same window, no prioritization will be made for scheduled and unscheduled visits.
 
FAS will be analyzed based on assigned arms.
 
Subgroup variables updated
 
New baseline characteristics added, and some characteristics had categories adjusted.
 
Baseline AD class data source changed from IRT reported to eCRF reported.
 
Imputation rule defined for MDE start date
 
Added rules for unblinded patient handling
 
MAOIs added as prohibited medication
 
Endpoint related to patient discontinued study or need new treatment was dropped since the information was covered in disposition and IE listings.
 
The term TEAE was changed to AE for simplicity
 
AE summary by SMQ not applicable and deleted
 
Separate summary of death/ fatal AE was removed since those was covered by SAE outputs
 
AESIs were summarized separately on dosing day and overall
 
Updated summary for newly occurring and worsening lab parameters
	
Section 2.1.2
 
Section 2.2
 
Section 2.2.1
 
Section 2.3.2
 
Section 2.3.3
 
Section 2.4.1
 
Section 2.4.2.2
 
Section 2.6.1.1
 
Section 2.7.1
 
Section 2.7.3 and Section 5.3

Date	Time point	Reason for update	Outcome for update	Section and title impacted (Current)
			Removed detailed CTCAE grade table in the Appendix since the standard macro will be applied	
			Boxplot for change from baseline in Component scores of CADSS was dropped and values were listed instead.	Section 2.7.4.3
			Sankey plots changed to stacked bar chart	Section 2.7.4.4 and Section 2.12
			C-SSRS summary changed to use standard table and listing	Section 2.7.4.5
			Details added for dose proportionalities	Section 2.8.3
			AE/CM imputation rules were deleted and were covered in PDS.	Section 5.1
			[REDACTED]	[REDACTED]
19-Aug-2022	Prior to DB lock	Creation of final version	First version	NA

**List of abbreviations**

AE	Adverse Event
AESI	Adverse Events of Special Interest
ANCOVA	Analysis of Covariance
ATC	Anatomical Therapeutic Chemical classification
CADSS	Clinician-Administered Dissociative States Scale
████	████████████████████████████████████████
████	████████████████████████████████████████
CRF	Case Report Form
CRS	Case Retrieval Strategy
CS	Compound Symmetry
CSR	Clinical Study Report
C-SSRS	Columbia Suicide Severity Rating Scale
CT.GOV	ClinicalTrials.gov
CTCAE	Common Terminology Criteria for Adverse Events
DMC	Data Monitoring Committee
DMS	Document Management System
DR	Dose Response
████	████████████████████████████████████████
████	████████████████████████████████████████
EOS	End of Study
EudraCT	European Union Drug Regulating Authorities Clinical Trials
FAS	Full Analysis Set
FWER	Family-wise Error Rate
IA	Interim Analyses
IE	Intercurrent Events
IRT	Interactive Response Technology
████	████████████████████████████████████████
LoE	Lack of efficacy
LS-means	Least Squares Means
████	████████████████████████████████████████
MADRS	Montgomery Asberg Depression Rating Scale
MAR	Missing at Random
████	████████████████████████████████████████
████	████████████████████████████████████████
MedDRA	Medical Dictionary for Drug Regulatory Affairs
MI	Multiple Imputation
MMRM	Mixed-effects Model for Repeated Measures
MNAR	Missing Not at Random
MOAA/S	Modified Observer's Assessment of Alertness/Sedation
PD	Protocol Deviations
PDS	Programming Dataset Specification

PK	Pharmacokinetics
PPS	Per-Protocol Set
PT	Preferred Term
RAP	Reporting & Analysis Process
s.c.	subcutaneous
SAE	Serious Adverse Events
SAF	Safety Set
SAP	Statistical Analysis Plan
SAS	Statistical Analysis System
SD	Standard Deviation
SMQ	Standardized MedDRA Query
SNRI	Serotonin–Norepinephrine Reuptake Inhibitor
SoC	Standard of Care
SOC	System Organ Class
SSRI	Selective Serotonin Reuptake Inhibitor
TEAE	Treatment-emergent Adverse Events
TFLs	Tables, Figures, Listings
TRD	Treatment Resistant Depression
WHO	World Health Organization

## 1 Introduction

The purpose of this statistical analysis plan (SAP) is to provide details of the statistical analysis described in [\[Section 12\]](#) of the Protocol v02 (release date: 04-Nov-2022) for study CMIJ821B12201.

This SAP includes the detailed plans for the primary, secondary [REDACTED] objectives of the study as well as supplementary analyses for the primary objective and associated sensitivity analyses. All the statistical analysis results based on this SAP will be reported in the final Clinical Study Report (CSR). The analysis mentioned in this SAP will be performed by Novartis internal statisticians and programmers, if not specified differently.

### 1.1 Study design

This is a Phase IIa non-confirmatory, randomized, double-blind, placebo-controlled, parallel-group trial in participants with Treatment-Resistant Depression (TRD) to evaluate the efficacy, safety, tolerability, and pharmacokinetics of subcutaneous (s.c.) MIJ821 administration in addition to pharmacological antidepressant standard of care (SoC) treatment. The study design is illustrated in [Figure 1-1](#).

Participants will be randomly allocated to one of the following four treatment arms in a 1:1:1:1 ratio:

- Single administration of MIJ821 s.c. 10 mg;
- Single administration of MIJ821 s.c. 4 mg;
- Single administration of MIJ821 s.c. 1 mg;
- Single administration of Placebo s.c..

The screening period starts when the participant signs the informed consent form and can last up to 28 days. The eligibility of participants is determined based on the assessments performed during the screening period and also on Day 1 (baseline/ prior to randomization).

Approximately 56 participants will be randomized to one of the above treatment arms via Interactive Response Technology (IRT) on Day 1/pre-dose in a blinded manner. The randomization will be stratified by the class of baseline anti-depressant SoC, which includes three categories: i) Selective Norepinephrine Reuptake Inhibitors (SNRI); ii) Selective Serotonin Reuptake Inhibitors (SSRI) and iii) other anti-depressants or any combinations.

In all treatment arms, the investigational treatment (MIJ821 or Placebo) is administered as a single s.c. injection on Day 1, followed by a safety observation at the clinical site for a minimum of 4 hours after administration. Details of the safety assessments and release criteria can be found in the protocol.

The post-dose follow-up period will continue for 4 weeks (28 days) after treatment. On-site visits to assess efficacy and safety are scheduled on Day 2 (24 hours post-dose) and

[figure not shown]
subsequently every week (i.e., on Days 8, 15, 22 and 29) during the follow-up period. The assessment to address the primary objective will be performed at Day 2 (24 hours post-dose). End-of-study (EOS) visit will be completed on site on Day 29. Phone calls will be conducted 3 days after each on-site visit (except for the EOS visit) to collect safety data including any AEs and concomitant medication use. The total duration of the study is approximately 8 weeks (56 days), including screening.

Safety monitoring will be conducted during the study using an independent Data Monitoring Committee (DMC). The analysis plan for DMC analysis will be covered in a different SAP.

All analysis covered in this SAP will be completed after the final database lock (DBL).

**Figure 1-1 Study design**

[figure not shown]
## 1.2 Study objectives, endpoints and estimands

Study objectives and related endpoints are described in [Table 1-1](#) below. More details about the primary estimands are discussed in [Section 1.2.1](#).

**Table 1-1 Study objectives and related endpoints**

Objective(s)	Endpoint(s)
Primary objective(s) • To assess efficacy of MIJ821 (versus placebo) in treatment resistant depression after single s.c. injection	Endpoint(s) for primary objective(s) • MADRS total score at 24 hours after s.c. injection compared to baseline assessment

Objective(s)	Endpoint(s)
Secondary objective(s) 

● To assess safety and tolerability of MIJ821 after single s.c. injection
 
● To assess MIJ821 PK in plasma after single s.c. injection
 
● To assess the duration of antidepressant effect of MIJ821

● To characterize the dose-response and exposure-response relationship of MIJ821

	Endpoint(s) for secondary objective(s) 

● Incidence and severity of treatment-emergent adverse events (TEAEs), including AEs of special interest; standard safety assessments such as vital signs, ECG, hematology, blood chemistry, urinalysis; Clinician-Administered Dissociative States Scale (CADSS) score, Modified Observer's Assessment of Alertness/Sedation (MOAA/S), C-SSRS, memory assessment using orientation questions, results of local tolerability assessments

● PK properties of MIJ821 in plasma described by Area under the curve from time zero to time of last measurable concentration (AUClast), maximum plasma drug concentration (Cmax), time to reach maximum plasma concentration (Tmax) (parameters not limited).

● MADRS total score at Day 8, 15, 22 and 29 visits compared to baseline

● Dose-response relationship of MIJ821 with respect to change from baseline in MADRS total score at 24 hours after single s.c. injection

● Exposure-response relationship of MIJ821 with respect to change from baseline in MADRS total score at 24 hours (Day 2)

### 1.2.1 Primary estimand(s)

The primary clinical question of interest is: What is the effect of s.c. MIJ821 (versus placebo) given in addition to standard pharmacological antidepressant (SoC) treatment 24 hours after the injection of the study drug on change in depressive symptoms in participants with TRD, who have already failed to adequately respond to at least two conventional antidepressants.

The justification for the primary estimand is that it will allow to estimate the rapid effect of the study drug in a population of depressed participants, who are considered treatment resistant, based on the definition above. A rapid response is clinically valuable as conventional antidepressants might need several weeks to achieve reduction of depressive symptoms.

The primary estimand is described by the following attributes:

1. Population: participants with treatment-resistant depression, who have failed to show adequate treatment response to at least 2 antidepressants previously.
2. Primary variable/endpoint: change from baseline in MADRS total score at 24 hours post-dose.
3. Treatment of interest: the randomized treatment (the investigational treatment MIJ821 or the placebo treatment) administered as a single s.c. injection on Day 1. The dose of the allowed concomitant medication (i.e., SoC) for depression must remain stable during the trial.
4. Handling of intercurrent events (IEs) prior to MADRS assessment at 24 hours:
  - New intake or change in concomitant medications/therapies which have a potential confounding effect: hypothetical strategy
  - Intake of prohibited medications: hypothetical strategy
  - Intake of rescue medications: hypothetical strategy
  - IEs related to pandemic: hypothetical strategy
  - IEs leading to study discontinuation due to adverse events (AEs), lack of efficacy or other reasons: treatment policy

The summary measure: difference in variable means between study drug and placebo.

## **2 Statistical methods**

### **2.1 Data analysis general information**

Unless otherwise specified, the analysis results based on this SAP will be reported in the final CSR. The full scope of analysis will be performed by Novartis.

Analysis pertaining to Data Monitoring Committee (DMC) activities will be covered in a separate SAP.

Statistical analysis will be performed using SAS® statistical software (SAS Institute, Cary, NC, USA.) version 9.4 or later, and R version 4.1.0 or above.

Unless otherwise specified, summary tables/listings/figures will be presented for each treatment arm in the respective analysis set. In general, data of interest will be listed by treatment arm and by country/center number/subject id (/period/visit wherever applicable).

In general, assessments at scheduled visits will be analyzed (unless specified otherwise) and presented in Tables and Figures after visit remapping using analysis windows defined in [Section 2.1.2](#). The assessment schedule is defined in protocol [[Table 8-1](#)], thus will not be repeated in this SAP. Listings will include both scheduled and unscheduled visits.

Categorical data will be presented as frequencies and percentages. For continuous data, the number of non-missing observations, mean, standard deviation (SD), median, minimum and maximum will be presented. For selected parameters, 25th and 75th percentiles may also be presented. P-values will be presented only if a formal hypothesis test is performed.

General information on treatment arm handling, decimal places and other output-related information will be specified in tables, figures and listing (TFLs) shells accompanying this analysis plan.

#### **2.1.1 General definitions**

##### **2.1.1.1 Terminology – study drug**

###### **Study drug (treatment)**

The study drug or study treatment refers to the medication MIJ821 or Placebo.

###### **Standard of care (SoC)**

Patients are expected to receive pharmacological antidepressant SoC treatment starting before screening. The class of the dominant antidepressant drug (SNRI, SSRI and other antidepressants or any combinations) will be judged by physicians at baseline and used as stratification factor during randomization. The drugs and dosages used in SoC should be maintained during the entire study. Any change in SoC during the study must be documented in eCRF concomitant medication page with detailed date, time and indication. To be accurate,

the actual class of baseline antidepressants, which is based on the reported medications in the eCRF concomitant medication page, will be used in all the summary and analysis unless otherwise specified.

### **2.1.1.2 Study days and baseline derivation**

#### **Day 1**

Day 1 or reference start date is defined as the day of dose administration (s.c. injection of the study drug). For participants who are randomized but not dosed, the Day 1 refers to the date of randomization.

#### **Study day**

The study day of a specific date of interest is calculated relative to Day 1 as follows:

Before Day 1: Study day = (Date of interest – Date of Day 1).

On or after Day 1: Study day = (Date of interest – Date of Day 1) + 1.

Note that there is no Day 0, the day before Day 1 is referred as Day -1.

Duration of an event is calculated as (event end date – event start date) + 1.

#### **Baseline**

Ideally the baseline values should be assessed at 1 hour before treatment on Day 1. In the analysis, a baseline value is defined as the last evaluable measurement prior to the study drug injection, irrespective of re-screening. In this case, baseline values will be the values obtained as the last valid pre-dose assessment on Day 1. If there is no valid assessment on Day 1, an earlier visit (scheduled or unscheduled) closest to the Day 1 visit will be picked and the last valid assessment on that day will be considered as baseline.

The actual assessment time (if available) should be used when comparing multiple records on the same day. If actual time is not available, the planned time point should be used. If neither applies, the last valid record (i.e. the one with the largest record number) will be used. More programming details will be provided in the Programming Data Specification (PDS).

#### **Date of last contact**

For participants who die during the study, the death date will be used as the date of last contact. For other participants, the date of last contact will be derived as the last visit assessment date.

#### **Analysis cut-off date**

All available data will be used. Data after withdrawal of consent will be excluded from all TFL outputs.

#### **Treatment-emergent data**

The treatment-emergent data is defined as data collected after the study drug injection on Day 1. Considering the short follow-up duration (29 days after baseline) of this study, all safety data

after study treatment (except those collected after participant's withdrawal of consent) will be considered treatment-emergent. Similarly, the on-treatment period for the participants are defined as the whole study period from dose on Day 1 to EOS.

### 2.1.2 Analysis visit and windows

Since the actual visit for a participant may not exactly coincide with their targeted visit date, the actual visit date will be mapped to an analysis visit for the purpose of data summary and model analysis. For multiple assessments performed at different time points on the same day (e.g. 0.5h, 1.5h and 4h on Day 1), there's no need to remap the time points and analysis will be performed based on the site collected time points.

The visit window below in [Table 2-1](#) will be applied for efficacy endpoints (e.g. MADRS, [REDACTED]), safety endpoints (e.g. vital signs, C-SSRS and MOAA/S) and [REDACTED].

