Guidance issued by local regulatory bodies on this aspect prevail and must be implemented and appropriately documented (e.g. the presence of an impartial witness, sign/dating separate ICFs by trial participant and person obtaining informed consent, etc.).

8 Visit schedule and assessments

The Assessment Schedule (Table 8-1) lists all study assessments and when they are performed. All data obtained from these assessments must be supported in the participant's source documentation.

Participants should attend on-site study visits as outlined in the assessment schedule (Table 8-1) or as close to the designated day/time as possible. This is especially important for the Day 2 visit at which primary efficacy assessments are performed. Missed or rescheduled visits should not lead to automatic discontinuation. In addition, the participant will be contacted by phone in between on-site visits (Follow-up call) to collect information about adverse events and concomitant medications. In case follow-up calls have to be shifted by +/- 3 days, follow-up calls can be replaced by on-site visits in accordance to the original visit schedule.

In case a visit is performed outside the schedule, subsequent visits shall be performed in accordance to the original visit schedule. In addition to the scheduled visits, participants may have unscheduled visits for safety monitoring purposes at the discretion of the Investigator. Data collected during unscheduled visits will be recorded in the unscheduled visit CRFs.

Participants who discontinue from the study or withdraw their consent/oppose the use of their data/biological samples should be scheduled for a final evaluation visit if they agree, as soon as possible, at which time all of the assessments listed for the final visit will be performed. At this final visit, the adverse events and concomitant medications not previously reported must be recorded on the CRF.

The "X" in the table denotes the assessments to be recorded in the clinical database or received electronically from a vendor. The "S" in the table denotes the assessments that are only in the participant's source documentation and do not need to be recorded in the clinical database.

Every effort will be made to draw the PK samples at the protocol specified timepoints. Other assessments (e.g., ECG, vital signs, etc.) will be taken prior to the PK sample.

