**Table 2-2 Analysis visit windows for Laboratory**

Study visit	Target day (time)	Study day window
Baseline	1 (-1 h)	Day -28 to Day 1 pre-dose
24 hours	2	Day 1 post-dose to Day 4
Day 29	29	5 - EOS

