#### 2.5.1.1 Derivation of MADRS total score

The MADRS consists of 10 items that cover all the core depressive symptoms (apparent sadness, reported sadness, inner tension, sleep, appetite, concentration, lassitude, interest level, pessimistic thoughts, and suicidal thoughts). Each item is scored from 0 (item is not present or is normal) to 6 (severe or continuous presence of the symptom). For each item, a higher score represents a more severe condition.

The MADRS score will be measured at Screening, Baseline (Day 1, -1 hour), 4-hour post-dose on Day 1, 24 hours post-dose and follow-up visits on Day 8, Day 15, Day 22 and Day 29 (EOS).

The 4-hour post-dose assessment will use the '4-hour' questionnaire which is based on participant's condition as observed over the past 4 hours. Two items (reduced sleep and reduced appetite) are not applicable for 4-hour post-dose assessment and will be imputed based on the value of respective 1-hour pre-dose assessment.

[figure not shown]
The 24 hours post-dose assessment is based on the participant's condition as observed since the last evaluation. For all other assessments, a 7-day recall period is used.

A total score (ranges from 0 to 60) is calculated by adding the scores of all 10 items. The following proration formula will be applied to calculate the total score in the case when one of the item scores is missing:

[figure not shown]
$$\text{Total score} = \text{Sum of scores from items present} * (10 / \text{number of items present}).$$

Otherwise if 2 or more items are missing, the total score will be set to missing.

[REDACTED]

[REDACTED]

[REDACTED]

[REDACTED]

[REDACTED]

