## 2.6 Analysis supporting secondary objective(s)

### 2.6.1 Efficacy endpoint(s)

#### 2.6.1.1 Duration of antidepressant effect of MIJ821

##### Change from baseline in the MADRS total score over time

Derivation of the MADRS total score is covered in [Section 2.5.1.1](#). The change from baseline in MADRS total score will be summarized for all collected data (including 4-hour post-dose) by visit/timepoint and by treatment arms. In case of unblinding, the MADRS scores collected after patient's unblinding will be excluded in all the analysis. A listing of MADRS total score for each participant at each visit will be provided by treatment arm.

The change from baseline in MADRS total score at follow-up visits on Day 1 4 h post-dose, Day 2, 8, 15, 22 and 29 will be analyzed using the mixed-effects model for repeated measures (MMRM). This model will include the fixed, categorical effects of treatment, time (i.e. analysis visits), baseline MADRS score, class of anti-depressant standard of care, treatment-by-time and baseline MADRS score-by-time interactions. [REDACTED]

A summary table with model estimated means and their differences of each MIJ821 doses vs. placebo, will be obtained at each visit/timepoint, along with the 90% CI for the difference. Model estimated treatment means in change from baseline in MADRS score ( $\pm$ SE) will be plotted over time/visit for each arm.

[REDACTED TABLE]

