## 2.9 PD and PK/PD analyses

[figure not shown]
The exposure response relationship will be presented graphically for PK exposure parameters (e.g. Cmax and AUClast) and the change from baseline MADRS score derived at 24 h postdose and Day 8, Day 15, Day 22 and Day 29 during the follow-up.

[figure not shown]
Correlations will be assessed using statistical analysis methods (e.g. trendline analysis methods) and simple exposure response models (e.g. Sigmoid Emax models). Scatter plots of change from baseline of MADRS score (y-axis) versus PK exposure parameter (x-axis) will be provided by visit and the fitted lines and 90% pointwise confidence intervals from both the trendline analysis and Sigmoid Emax model will be added in the plots separately for each visit.

The hill parameter in the Sigmoid Emax models will be estimated if data allows. In case the model dose not converge, the Emax model with hill parameter equals 1 will be used. A table with estimated placebo effect and estimated parameters from the Sigmoid Emax models will be presented by visit.

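### Does mapping a MADRS score taken on study Days 3-4 to Day 8 distort the duration-of-effect analysis?

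*SAP*

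**What the plan says.** SAP Section 2.1.2 states that "the actual visit date will be mapped to an analysis visit for the purpose of data summary and model analysis", and that the Table 2-1 windows "will be applied for efficacy endpoints (e.g. MADRS" and further scales). Table 2-1 gives:

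| Analysis visit | Target day | Study days |
|---|---|---|
| 24 hours | 2 | 2 |
| Day 8 | 8 | 3 to 11 |
| Day 15 | 15 | 12 to 18 |
| Day 22 | 22 | 19 to 25 |
| Day 29 | 29 | 26 to EOS |

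Laboratory and ECG data have their own tables. For laboratory data the 24-hour window is "Day 1 post-dose to Day 4"; for ECG it is Days 2 to 4.

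The Day 8 label feeds two analyses. In SAP Section 2.6.1.1, change in MADRS at the 4-hour time point and at "Day 2, 8, 15, 22 and 29 will be analyzed using the mixed-effects model for repeated measures". SAP Section 2.9 plots exposure against change in the "MADRS score derived at 24 h postdose and Day 8, Day 15, Day 22 and Day 29".

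On recall periods, SAP Section 2.5.1.1 gives the 4-hour form a 4-hour recall and the 24-hour form a recall since the last evaluation. Then: "For all other assessments, a 7-day recall period is used".

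**The concern.** Three things make the Day 8 window look wrong.

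- **Distance.** Day 3 is one day from the 24-hour target and five from Day 8; Day 4 is two and four. The later boundaries in the table coincide with midpoints between targets, and this one does not.
- **Comparison.** For laboratory and ECG data the SAP puts Days 3-4 under the 24-hour visit.
- **Meaning.** A late 24-hour form asks about the time since the last evaluation. A final evaluation held on Day 3 or 4 uses a 7-day recall that is mostly pre-dose. Neither measures the effect at one week.

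At stake is the Day 8 estimate in the duration-of-effect MMRM, a stated secondary objective with about 14 participants per arm, and the Day 8 exposure-response plot. The error could go either way. A late 24-hour form overstates the Day 8 effect if the effect fades; a mostly pre-dose recall understates it. The primary 24-hour analysis is not in question. A natural remedy would be to open the MADRS Day 8 window on Day 5.

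**Working it through.** **1. The boundaries.** Targets are Days 2, 8, 15, 22 and 29 (SAP Table 2-1).

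- Midpoints: (2+8)/2 = 5; (8+15)/2 = 11.5; (15+22)/2 = 18.5; (22+29)/2 = 25.5.
- The table splits at 2/3, 11/12, 18/19 and 25/26. The last three agree with the midpoints; the first does not.
- The last three also follow from plus or minus 3 days around weekly targets, so they do not show that a nearest-target rule was adopted.
- The laboratory and ECG tables have no Day 8 row. Their next target is Day 29, and (2+29)/2 = 15.5, yet they split at 4/5. They do not follow the midpoint rule either.

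**2. When such a score can arise.** Protocol Table 8-1 schedules no MADRS between Day 2 and Day 8; Day 4 is a telephone call. Two routes remain.

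- *Late 24-hour visit.* Protocol Section 8 stresses that the Day 2 visit be on time. After an off-schedule visit, "subsequent visits shall be performed in accordance to the original visit schedule". The participant is still due a true Day 8 score.
- *Early final evaluation.* A participant who leaves the study "should be scheduled for a final evaluation visit if they agree, as soon as possible". That can be the only score in Days 3-11.

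The Day 3-4 score is certain to become the Day 8 value only when no other MADRS falls in Days 3-11. Otherwise the outcome depends on the rule for several records in one window. The SAP's document history shows this was addressed, but the operative text is not visible.

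**3. Size of one such score.** Inputs: 14 per arm (SAP Section 3); a difference of 8.25 points, from the pooled 0.16 mg/kg i.v. group of the proof-of-concept study (Protocol Section 1.1.3), used as an illustration; SD 8 to 12, assumed because no SD is visible.

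- Late 24-hour form, with 25%, 50% or 100% of the effect gone by Day 8: 8.25 × (0.25, 0.5, 1)/14 = 0.15, 0.29, 0.59 points on the arm mean.
- Early final evaluation, assuming a sustained effect and time-weighted recall: the post-dose share of 7 days is 2/7 = 29% on Day 3 and 3/7 = 43% on Day 4. The shift is 8.25 × (5/7)/14 = 0.42 or 8.25 × (4/7)/14 = 0.34 points, in the opposite direction.
- SE of a two-arm difference: SD × √(2/14) = 3.02 (SD 8) or 4.54 (SD 12).
- In SE units: late form at most 0.59/3.02 = 0.20 (SD 8) or 0.59/4.54 = 0.13 (SD 12); final evaluation from 0.34/4.54 = 0.07 to 0.42/3.02 = 0.14.

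**4. Keeping against dropping the score.** In units of SE squared, on raw means:

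| Option | Added to mean squared error |
|---|---|
| Keep, late form, full fading, SD 8 | (0.59/3.02)² = 0.038 |
| Keep, late form, full fading, SD 12 | (0.59/4.54)² = 0.017 |
| Keep, final evaluation | 0.07² to 0.14² = 0.005 to 0.02 |
| Drop | (1/14 + 1/13)/(2/14) − 1 = 0.038 |

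Dropping the score breaks even only in the most extreme case and costs more in the others.

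**The case for a change.** The best case for a change is that the label is wrong on its face, one footnote would correct it, and settling the matter before unblinding removes a later choice. A strict Day 2 window for the primary endpoint does not oblige anyone to call Day 3 a one-week score. The variance comparison uses raw means, whereas the MMRM would recover part of a dropped score from the participant's other visits, so dropping costs somewhat less than shown. Squared bias also grows faster than the variance cost. With two fully faded late forms in one arm, keeping them adds 4 × 0.038 = 0.15, against (1/14 + 1/12)/(2/14) − 1 = 0.083 for dropping them.

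The description of the label stands, and so does the point about the MMRM. The two-record case needs two participants in one arm to attend late, both to have no true Day 8 score used, and the effect to have vanished by Day 8. For two early final evaluations, the likelier route, keeping adds at most 4 × (0.42/3.02)² = 0.08, no more than dropping.

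Opening the window on Day 5 also has faults of its own. Day 5 is three days from each target, and 3/7 = 43% of a 7-day recall is still pre-dose then. The last MADRS of an early discontinuer would leave the main MMRM, contrary to the general rule in SAP Section 2.1.1.2 to use all available data, and such people may leave for reasons tied to outcome.

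**Conclusion.** Table 2-1 does label a Day 3-4 MADRS as Day 8, but this is a fair trade-off. Once the 24-hour window is kept to Day 2, which suits a rapid-effect primary endpoint, the windows either run on without a gap or leave Days 3-4 unassigned. Windows without gaps are a defensible choice, and the alternative shows no clear net gain: at most 0.038 in squared-SE units from keeping one such score, against 0.038 from dropping it. This rests on the i.v. difference of 8.25 points carrying over, an SD of 8 to 12, 14 per arm and a single record; MMRM borrowing would reduce the cost of dropping it.

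The effect is confined to the secondary MMRM and the Day 8 exposure-response plot, its direction is not fixed, and there may be no such record. SAP Section 2.6.1.1 already provides a MADRS listing by participant and visit, and Section 2.1 says listings include unscheduled visits. Analysts can therefore look for a Day 3-4 score and, if one served as the Day 8 value, check the result without it. That is ordinary practice and needs no amendment.
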